2.2 Secondary Objectives

The secondary objectives of this study are to determine the:

- Progression-free survival (PFS) at 2 years after initiation of maintenance therapy
- Overall survival (OS) at 2 years after allogeneic stem cell transplant
- Incidence of graft-versus-host disease (GVHD) in patients receiving allogeneic stem cell transplant and maintenance with MLN9708
- Effect of MLN9708 on immune effector cells after allogeneic stem cell transplant.

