5. STUDY DESIGN

This is a Phase II, open-label, multicenter, non-randomized study to determine the feasibility of MLN9708 as maintenance after allogeneic stem cell transplant for multiple myeloma. Patients will be enrolled between Days 45 and 120 after allogeneic transplant and will receive MLN9708 on Days 1, 8, and 15 of each 28-day cycle for 6 cycles. Up to 18 patients will be enrolled in the dose-escalation phase to define the MTD of MLN9708. An additional 20 patients will be enrolled in the expansion phase at the MTD.

Up to 5 study sites are planned in the United States.

Dosing will start at 2.3 mg. If acceptable tolerability is demonstrated, escalations will be made to 3 mg and to the maximum-planned dose (MPD) of 4 mg. Once the MTD/MPD is determined, enrollment into the expansion phase will proceed at that dose. The study schema is presented in Figure 1.

[figure not shown]
CONFIDENTIAL

STUDY DRUG: MLN9708
FINAL PROTOCOL: 11 APRIL 2014
AMENDMENT NUMBER 3: 11 FEBRUARY 2016

SCRI INNOVATIONS STUDY NUMBER: MM 42

VERSION 4

Figure 1 Study Schema

MTD = Maximum-tolerated dose
MPD = Maximum-planned dose

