7.5 End-of-Treatment Visit

Patients are permitted to continue maintenance treatment with MLN9708 through 6 cycles. Patients may be discontinued before the end of 6 cycles due to disease progression, unacceptable toxicity, or the decision to discontinue treatment by the patient or the study physician. After withdrawal from or completion of protocol treatment, patients must be followed for any new AEs for 30 calendar days after the last dose of study drug.

Thirty days (± 3 days) days after completion of the planned study treatment period or early discontinuation, the following tests and observations will be conducted:

- Update of medical history
- Physical examination including a neurological evaluation, measurement of weight, and vital signs
- ECOG performance status
- Acute GVHD assessment with overall score
- Chronic GVHD assessment with overall score
- AE assessment
- Concomitant medication review of all medications taken for conditions other than GVHD
- Concomitant medication review specifically for GVHD prophylaxis since receiving the allogeneic transplant
- CBC, including 3-part differential (total neutrophil count including bands, lymphocytes, monocytes) hemoglobin, hematocrit, and platelets
- CMP to include: glucose, BUN, creatinine (creatinine clearance calculated by Cockcroft-Gault), sodium, potassium, chloride, calcium, phosphorus, magnesium, CO₂, ALT, AST, ALP, LDH, uric acid, total bilirubin, total protein, and albumin

CONFIDENTIAL

STUDY DRUG: MLN9708
 FINAL PROTOCOL: 11 APRIL 2014
 AMENDMENT NUMBER 3: 11 FEBRUARY 2016

SCRI INNOVATIONS STUDY NUMBER: MM 42

VERSION 4

- Urinalysis (dipstick; if abnormal microscopic performed as clinically indicated)
- Disease assessment:
 - Bone marrow aspirate and biopsy (to confirm CR only) including:
 - Quantify percent myeloma cell involvement
 - Obtain bone marrow aspirate for cytogenetics [i.e., diploidy, del 13] and include number of metaphases analyzed
 - Mutations detected in FISH studies [i.e., t(4:14); t(11:14); del 17p] to confirm CR
 - If available, provide MRD by flow cytometry
 - SFLC
 - SPEP and serum protein immunofixation to determine M-protein
 - UPEP, urine protein immunofixation (requires a 24-hour urine collection), and total protein in urine
 - Serum quantitative immunoglobulins
 - Known plasmacytomas, utilize same modality used to assess original disease (i.e., PET, MRI, CT, etc)

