10.4.2 Efficacy Analysis

- PFS, defined as the time from the first day of study drug administration (Day 1) to disease progression as defined by the International Myeloma Working Group Uniform Response Criteria (see Appendix E), or death on study. Patients who are alive and free from disease progression will be censored at the date of last tumor assessment.
- OS, defined as the time from the first day of study drug administration (Day 1) or death on study. Patients who are alive will be censored at the date of last known date alive.

Progression-free survival and OS (efficacy secondary endpoints) estimates will be generated using Kaplan-Meier methods, both for all patients enrolled and those patients receiving the MTD. Two-year PFS and OS estimates with 95% confidence intervals (CIs), and median PFS and OS with 95% CIs, will be generated and reported accordingly.

The effect of MLN9708 on immune effector cells after allogeneic stem cell transplant will be analyzed by examining the difference in the actual change from baseline at Cycle 1 Day 4, Cycle 1 Day 8, Cycle 1 Day 15, and Cycle 2 Day 1, and the percentage change from baseline at Cycle 1 Day 4, Cycle 1 Day 8, Cycle 1 Day 15, and Cycle 2 Day 1, among those patients participating in the biomarker research component. Each analysis will be performed within dose level and total patients.

The following parameters will be examined:

- CD3+, CD4+, CD8+, CD45+, CD19+ and CD56+/CD16+ cell counts, by fluorescence-activated cell sorting
- Regulatory T cell counts by intracellular staining of FoxP3, and surface staining of CD4+ and CD25+ cells
- Inflammatory cytokine concentrations of IL-1 β , IL-6, IL-8, IL-10 and TNF- α .

CONFIDENTIAL

STUDY DRUG: MLN9708

SCRI INNOVATIONS STUDY NUMBER: MM 42

FINAL PROTOCOL: 11 APRIL 2014

AMENDMENT NUMBER 3: 11 FEBRUARY 2016

VERSION 4

For each parameter, the actual change from baseline and the percentage change from baseline, at each time point, will be analyzed using the two-sided Wilcoxon signed-rank procedure to test whether either the change is statistically different from zero.

The significance level will be set at 10%, and there will be no adjustment to the alpha level for multiple comparisons. The rationale for the reporting of p-values in these analyses is for hypothesis-generating purposes only.

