11.3.4 Deaths

Deaths that occur during the protocol-specified AE reporting period that are attributed by the Investigator solely to progression of disease will be recorded on the “Study Discontinuation” eCRF screen. All other on study deaths, regardless of attribution, will be recorded on an SAE Report Form and expeditiously reported to the SCRI Innovations Safety Department.

When recording a SAE with an outcome of death, the event or condition that caused or contributed to the fatal outcome should be recorded as the single medical concept on the SAE Report Form and Adverse Event screen of the eCRF. If the cause of death is unknown and cannot be ascertained at the time of reporting, record “Death NOS” on the eCRF Adverse Event screen. During post-study survival follow-up, deaths attributed to progression of disease will be recorded only on the “After Progressive Disease Follow-Up” eCRF screen.

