Appendix D: MM 42 Schedule of Assessments

Procedures	Pre-TX	Cycle 1 Cycle = 28 days				Cycles 2 to 6 Cycle = 28 days			Reassess Every 2 Cycles (8 weeks)	End of Study Treatment ^f	Follow-up	
	Baseline	Day				Day					Off Study Prior to Progression ^s	After Disease Progression ^t
		1	4	8	15	1 (± 2 days)	8	15				
TESTS & OBSERVATIONS												
Written informed consent ^a	X											
Medical history ^b	X	X				X				X	X	
Physical examination ^{b,c}	X	X	X ^c	X ^c	X ^c	X				X	X	
ECOG performance status ^b	X	X				X				X	X	
GVHD assessment ^d	X	X		X ^d	X ^d	X	X ^d	X ^d		X	X	
12-lead ECG ^e	X											
Chest X-ray	X											
Adverse event evaluation		X	X	X	X	X	X	X		X	X	
Concomitant medications (GVHD and non-GVHD)	X	X	X	X	X	X	X	X		X	X	
Response assessment ^f									X ^e	X ^e	X ^e	
Survival status												X
LABORATORY TESTS												
CBC, 3-part diff & platelets ^{b,g}	X	X		X	X	X	X	X		X	X	
CMP ^{b,h}	X	X		X	X	X				X	X	
Urinalysis ^{b,i}	X	X		X	X	X				X		
PT/aPTT/INR ^b	X	X				X						
Serum or Urine β-HCG ^j	X											
Biomarker blood sample ^k		X	X	X	X	X						
Percentage chimerism ^l		X ^l				X ^l					X ^l	
DISEASE ASSESSMENTS												
Bone Marrow Aspira/Biopsy ^m	X								X ^m	X ^m		
Skeletal Survey ⁿ	X											
Serum free light chain	X								X ^q	X ^q	X ^q	
SPEP & immunofixation	X								X	X	X	
UPEP & immunofixation ^o	X								X	X	X	
Serum immunoglobulins	X								X	X	X	
Serum β-2 microglobulin	X											
Known plasmacytomas ^p	X								X	X	X	

CONFIDENTIAL

SCRI INNOVATIONS STUDY NUMBER: MM 42

STUDY DRUG: MLN9708

FINAL PROTOCOL: 11 APRIL 2014

AMENDMENT NUMBER 3: 11 FEBRUARY 2016

VERSION 4

-
- ^a Written informed consent must be obtained before any study-related procedure is performed and ≤ 28 days prior to the initiation of study treatment.
- ^b The Baseline visit physical examination, medical history (see Section 7.2), ECOG performance status, CBC, CMP, PT/aPTT/INR, and urinalysis should be done < 7 days prior to initiation of treatment. However, if these initial examinations are obtained ≤ 72 hours before first study treatment they do not have to be repeated on Day 1 of Cycle 1.

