Death while on-study without previous PD, and received no subsequent therapy	Date of death	Event																	
Death while on-study and had previous PD, and received no subsequent therapy	First date of evaluated overall response = PD	Event																	

	Death while on-study without previous PD, but received subsequent therapy prior to death event	Date of last evaluable tumor assessment prior to start of subsequent therapy	Censored
	Death while on-study and had previous PD, but received subsequent therapy prior to PD event	Date of last evaluable tumor assessment prior to start of subsequent therapy	Censored
	No progression, no death	Date of last evaluable tumor assessment	Censored
	Treatment discontinuation for adverse event or other non-event reason	Date of last evaluable tumor assessment	Censored
Overall Survival: Event = Death			
	Situation	Date of Event or Censoring	Outcome
	Death, while on-study or follow-up	Date of death	Event
	Alive, as of end of study or follow-up	Date last known alive	Censored
	Status unknown, as of end of study	Date last known alive	Censored
 Overall Response Rate (ORR)	Default: Estimates of rates in each treatment arm		
 Disease Control Rate (DCR)	 Difference in rates & 95% confidence interval between treatment arms		
 Clinical Benefit Rate (CBR)	 p-value, specify statistical test:		
 Early Progression Rate (EPR)			
 Time To Progression (TTP)	Default: Estimates of medians in each treatment arm		
 Progression-Free Survival (PFS)	 Other quartiles or percentages of survival required, specify: PFS, OS: 2 year PFS and OS with 95% confidence intervals		
 Overall Survival (OS)	 Hazard ratio & 95% confidence interval between treatment arms, unstratified		
 Duration of Response	 p-value, specify statistical test:		
 Duration of Stable Disease	 Hazard ratio & 95% confidence interval between treatment arms, stratified (specify stratification factor(s)):		
 Time To Treatment Failure (TTF)	 p-value, specify statistical test:		
 Other, Specify:			
7 Safety			

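### The PFS rules conflict on progression-free deaths in follow-up: read literally, the SAP event rows do not count them, and 2-year PFS would be biased upward

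*SAP*

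**What the plan says.** **PFS.** Protocol 10.4.2 counts progression "or death on study. Patients who are alive and free from disease progression will be censored at the date of last tumor assessment". SAP 1.2 repeats this. In SAP 5/6, Definition of Endpoints, the heading of the PFS table gives progression or death as the event, with no limit on when death occurs. All four death rows beneath it are limited to death while on study. The one that makes a progression-free death an event is "Death while on-study without previous PD, and received no subsequent therapy". A further row censors treatment discontinuation for an adverse event or other non-event reason at the last evaluable assessment, with no exception for a later death.

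**OS.** The definitions in Protocol 10.4.2 and SAP 1.2 also refer to death on study, but the event row in the SAP table is "Death, while on-study or follow-up".

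**Follow-up.** Appendix D heads the visits after treatment and before progression "Off Study Prior to Progression". Protocol 11.3.4 also separates on-study deaths from a later period: "During post-study survival follow-up, deaths attributed to progression of disease will be recorded only on the" after-progression screen of the eCRF. Neither document defines 'on study'.

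**The concern.** The PFS and OS tables sit in the same section. One names on-study death only; the other names on-study and follow-up death. A programmer working row by row could fairly conclude that the two periods differ and that follow-up deaths belong to OS alone. Another, working from the heading, would count them for PFS as well. The two would report different 2-year PFS from the same data.

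The objective is "Progression-free survival (PFS) at 2 years after initiation of maintenance therapy", while planned treatment lasts 24 weeks, so most of the window lies after treatment. Protocol 1.2.8 itself says that allogeneic transplant carries higher mortality through complications of GVHD, so death without progression is an expected way to fail. If those deaths are censored, the endpoint after the end-of-treatment visit becomes time to progression, and a patient can be dead for OS yet censored as progression-free for PFS. There is no control arm in which the bias could cancel.

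**Working it through.** The documents give no figure for this point: no PFS power, event target or on-study share. The check has three parts.

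**1. Which row applies?** Take a patient who completes six cycles, has no progression and no subsequent therapy, and dies at month 14.

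| Rule | Applies? |
|---|---|
| PFS table heading | Yes: event |
| On-study death, no PD, no subsequent therapy | Only if follow-up is on study |
| No progression and no death | No: the patient died |
| Treatment discontinuation, non-event reason | Unclear for a completer; yes for an early stopper |
| Narrative censoring rule | No: it covers only patients who are alive |
| OS event row | Yes: event |

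With 'on study' read narrowly, no PFS event row fits. The completer is unassigned and the early stopper is censored.

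**2. How much of the window is affected?**

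- Landmark: 2 years = 730 days from first dose (Protocol 2.2).
- Treatment: patients "will receive MLN9708 on Days 1, 8, and 15 of each 28-day cycle for 6 cycles" (Protocol 5), so 6 × 28 = 168 days.
- End-of-treatment visit: "Thirty days (± 3 days) days after completion of the planned study treatment period or early discontinuation" (Protocol 7.5), so 168 + 30 = Day 198, or Day 195 to 201 with the visit window.
- Share after the visit: (730 − 198)/730 = 532/730 = 72.9% (72.5% to 73.3% with the visit window).
- Protocol 7.4 continues disease assessments for 2 years after maintenance, to about Day 168 + 730 = 898, so planned follow-up covers the landmark.

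The share depends on where on-study time is taken to end:

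| On-study time ends at | Day | Share after |
|---|---|---|
| End of cycle 6 | 168 | 77.0% |
| Last planned dose (Day 155) + 30 | 185 | 74.7% |
| End-of-treatment visit | 198 | 72.9% |
| Same, one 3-week delay | 219 | 70.0% |
| Same, 3-week delay before each of cycles 2 to 6 | 303 | 58.5% |
| Stop after cycle 1 (28 + 30) | 58 | 92.1% |

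**3. How large would the bias be if these deaths were censored?** Assume constant hazards, a completer's timeline, and a rate r per year of progression-free death without subsequent therapy. The documents give no such rate. Let Hp and Hd be the 2-year cumulative hazards of progression and progression-free death.

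- True 2-year PFS = exp(−Hp − Hd)
- Reported 2-year PFS = exp(−Hp − Hd × 198/730)
- Ratio = exp(r × 532/365) = exp(1.458 r)

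| Assumed r | Ratio | A true 50% reads as |
|---|---|---|
| 5% per year | exp(0.0729) = 1.076 | 53.8% |
| 10% per year | exp(0.1458) = 1.157 | 57.8% |
| 15% per year | exp(0.2187) = 1.244 | 62.2% |

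A second set of assumptions, with 2-year progression of 30% to 50% and 2-year progression-free death of 5% to 20%, gives an increase of 1.8 to 9.9 percentage points. For example, with 40% progression and 10% death, true PFS is 0.60 × 0.90 = 54.0%, and the reported value is 0.60 × 0.90^(198/730) = 58.3%.

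**The case against.** A reader might infer that the plan flatly excludes follow-up deaths from PFS. The documents do not settle that, and the case against it is substantial.

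- The PFS table heading counts any death.
- The narrative rule censors only patients who are alive, so it cannot censor someone who has died.
- The OS definitions use the same on-study wording, yet the OS table includes follow-up, so in the narratives the phrase may extend past treatment.
- Some PFS rows describe on-study death after subsequent therapy or after PD. Protocol 5.3.2 withdraws patients before other anticancer agents are given, and Protocol 7.4 takes patients with PD off study. Under a narrow meaning of on study, those rows would be nearly empty.
- The Appendix D footnote describes the pre-progression follow-up group as patients who stopped study treatment, so the column label may mean off treatment. It is a visit label, not an endpoint definition.
- The post-study sentence in 11.3.4 is a safety-reporting rule about deaths attributed to progression, not progression-free deaths.

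All of this stands, and it limits the claim to a conflict between rules. It does not remove the conflict. The OS row names follow-up and the PFS rows do not. Protocol 7.4 and the SAP also take patients with unacceptable toxicity off study, and the discontinuation row censors with no exception for later death.

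**Conclusion.** The concern holds as a conflict between rules. 'On study' is undefined, the heading and narratives favour counting progression-free follow-up deaths, and the rows read literally do not count them. Such a death is unassigned in a completer and censored by the discontinuation row in a patient who stopped early.

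The 73% is calendar time for an undelayed six-cycle patient. A reader might take it as a share of deaths or events, but the documents give no timing of deaths from which to derive one. The upward bias depends on the literal reading being applied. Its size, a true 50% read as about 54% to 62%, also rests on assumed death rates of 5% to 15% per year and constant hazards. Deaths after subsequent therapy are censored under separate rows on either reading and are not part of this effect.

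The SAP's efficacy table lists PFS as primary, but the protocol makes it a secondary objective, and there is no power calculation for it. The effect is on the 2-year estimate and its interval, not on sample size. It is a should-fix before analysis.

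**What to change.** 1. Reword the SAP's PFS row for progression-free death without subsequent therapy so that it covers death on study or in follow-up, matching the OS row. Date it at death and count it as an event.
2. Bring the PFS definitions in Protocol 10.4.2 and SAP 1.2 into line, and define 'on study' if the term is kept.
3. State that the treatment-discontinuation row applies only to patients with no later PD or death.
4. Leave the subsequent-therapy rows unchanged. A blanket rule counting death in every patient without prior PD would override them.
5. Confirm that death dates are captured in follow-up before progression: Appendix D marks survival status only in the after-progression column. OS needs these dates in any case.

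The cost is protocol and SAP wording plus one check of data capture. The downside is that reported 2-year PFS may be lower.

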9. RESPONSE EVALUATIONS AND MEASUREMENTS

Response and progression will be evaluated in this study using the International Myeloma Working Group Uniform Response Criteria (see Appendix E).

CR	Complete Response
sCR	subcategory: stringent complete response
VGPR	Very good partial response
PR	Partial response
SD	Stable disease
PD	Progressive disease

All response categories (CR, sCR, VGPR, PR, PD) require two consecutive assessments made at any time before the institution of any new therapy, as well as no known evidence of progressive or new bone lesions if radiographic studies were performed. Radiographic studies are not required to satisfy these response requirements. Bone marrow assessments are not required to be confirmed by repeat testing.

Complete response should be confirmed with a bone marrow biopsy for morphology and a bone marrow aspiration for flow cytometry, FISH, and cytogenetics performed locally. Additional confirmatory studies include SPEP, UPEP, immunofixation of blood and urine, and SFLC (see Appendix D).

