Definition of Endpoints:	Start Date:  Date of Randomization  Date of First Treatment End Date (specify for all pertinent endpoints): Progression-Free Survival: Event = Progression or Death 
  
 Situation	Date of Event or Censoring	Outcome	
   
 No baseline assessment	Date of first treatment	Censored	
 
 PD documented between scheduled visits, did not die, and received no subsequent therapy	First date of evaluated overall response = PD	Event	
 
 PD documented between scheduled visits, did not die, but received subsequent therapy prior to incurring progression event	Date of last evaluable tumor assessment prior to start of subsequent therapy	Censored	
 
 Death while on-study without previous PD, and received no subsequent therapy	Date of death	Event	
 
 Death while on-study and had previous PD, and received no subsequent therapy	First date of evaluated overall response = PD	Event	
  
	Situation	Date of Event or Censoring	Outcome	No baseline assessment	Date of first treatment	Censored	PD documented between scheduled visits, did not die, and received no subsequent therapy	First date of evaluated overall response = PD	Event	PD documented between scheduled visits, did not die, but received subsequent therapy prior to incurring progression event	Date of last evaluable tumor assessment prior to start of subsequent therapy	Censored	Death while on-study without previous PD, and received no subsequent therapy	Date of death	Event	Death while on-study and had previous PD, and received no subsequent therapy	First date of evaluated overall response = PD	Event
Situation	Date of Event or Censoring	Outcome																	
No baseline assessment	Date of first treatment	Censored																	
PD documented between scheduled visits, did not die, and received no subsequent therapy	First date of evaluated overall response = PD	Event																	
PD documented between scheduled visits, did not die, but received subsequent therapy prior to incurring progression event	Date of last evaluable tumor assessment prior to start of subsequent therapy	Censored																	

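### The SAP's PFS table censors on-study deaths that follow subsequent therapy, contrary to the written PFS definition, and has no row for progression followed by therapy

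*SAP*

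**What the plan says.** Protocol 10.4.2 runs PFS from the first dose to progression by the myeloma criteria of Appendix E, or to death on study. Its only censoring rule is "Patients who are alive and free from disease progression will be censored at the date of last tumor assessment". SAP 1.2 repeats both. Neither mentions subsequent therapy in the definition.

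SAP section 5/6 (Definition of Endpoints) opens its table with "Progression-Free Survival: Event = Progression or Death". The rows then bring subsequent therapy in.

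- **Event rows.** "PD documented between scheduled visits, did not die, and received no subsequent therapy"; "Death while on-study without previous PD, and received no subsequent therapy"; "Death while on-study and had previous PD, and received no subsequent therapy".
- **Censoring rows tied to therapy.** "PD documented between scheduled visits, did not die, but received subsequent therapy prior to incurring progression event"; "Death while on-study without previous PD, but received subsequent therapy prior to death event"; and a third row for death after a progression that itself came after therapy. All three are censored at the last evaluable assessment before the therapy began.

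Two other places bear on this. Protocol section 9 says that response categories, with progression named among them, "require two consecutive assessments made at any time before the institution of any new therapy"; a footnote to Appendix E says the same of all categories. In the SAP's Definition of Terms, progression is taken from the investigator's report, and the box for defining subsequent therapy is unticked and blank.

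**The concern.** A patient who starts new therapy and then dies on study is not alive and progression-free, so the written definition gives no ground for censoring. The table censors that patient all the same, at a date earlier than the therapy. No rationale is given, and no sensitivity analysis is planned.

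The second problem is one of coverage. Documented progression followed by further treatment is a common course after relapse. Read literally, the event rows exclude it, because therapy was received. The censoring rows exclude it too, because the therapy did not precede the event. The programmer has to guess.

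Two-year PFS is a secondary objective, estimated by Kaplan-Meier in a single-arm study of at most 38 patients. Kaplan-Meier assumes that a censored patient has the same outlook as those still at risk. If new therapy is given because disease is returning, the censored patients have a worse outlook and the estimate is too high. There is no control arm in which the same bias could partly cancel.

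**Working it through.** **Step 1: compare the table with the definition, path by path.** The plan has no figure of its own to reproduce here, so the first check is logical. I read the table's phrase about progression between scheduled visits as covering any documented progression. Combining progression (PD), death and subsequent therapy gives ten patient paths.

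| Path | SAP table | Written definition, plain reading |
|---|---|---|
| No PD, alive, no therapy | Censored | Censored |
| No PD, alive, therapy | Censored | Censored |
| PD, alive, no therapy | Event | Event |
| PD, then therapy, alive | No row | Event |
| Therapy, then PD, alive | Censored | Event |
| Death, no PD, no therapy | Event | Event |
| Therapy, then death, no PD | Censored | Event |
| PD, then death, no therapy | Event | Event |
| PD, then therapy, then death | No row | Event |
| Therapy, then PD, then death | Censored | Event |

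Eight paths contain a progression or a death. The table makes 3 of them events, censors 3 and has no row for 2 (3 + 3 + 2 = 8).

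**Step 2: apply the pre-therapy condition of section 9 and Appendix E.** If a progression counts only when assessed before any new therapy, two entries in the right-hand column change:

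- Therapy, then PD, alive: no longer clearly an event, so censoring it has protocol support.
- Therapy, then PD, then death: still an event, but dated at death.

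The two paths that run from therapy to death, with or without PD between, are therefore events on either reading. The table censors both. That is the firm part of the contradiction.

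**Step 3: illustrate the size.** Inputs, all assumed because the documents give none:

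- S: true 2-year PFS under the written definition.
- f: share of PFS events that the table censors because therapy came first.
- A constant hazard.

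When a share f of events is turned into censoring shortly before it would have occurred, the apparent hazard is about (1 − f) times the true one. The estimate is then about S^(1 − f).

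- S = 0.50, f = 0.10: 0.50^0.90 = 0.536
- S = 0.50, f = 0.20: 0.50^0.80 = 0.574

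A simulation of 400,000 patients per scenario (exponential event times, follow-up cut at 30 months, affected patients censored 3 months before their event) gave these Kaplan-Meier estimates at 24 months:

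| True 2-year PFS | f = 10% | f = 20% |
|---|---|---|
| 40% | 43.4% | 47.3% |
| 50% | 53.4% | 56.9% |
| 60% | 63.0% | 66.1% |

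**Step 4: put it in patients.** With all 38 patients analysed and S = 50%, there are 38 × 0.50 = 19 events by two years. Then f = 10% is about 1.9 events and f = 20% about 3.8. Two to four reclassified patients would produce shifts of roughly 3 to 7 points.

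**The case against.** **Censoring at new therapy is a recognised convention.** It may have been intended, and PFS here is descriptive, with no test and so no error rate to protect. Sampling error is also large: with 38 fully followed patients and a rate of 50%, the approximate 95% half-width is 1.96 × √(0.25/38) = 0.159, about 16 points. All of this limits the weight of the point. It does not explain why the table departs from a definition that both documents state, and a wide interval does not excuse a bias in a known direction.

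**Such deaths may not be on study at all.** Protocol 5.3.2 requires withdrawal from the study before other anticancer agents are given, and neither document defines on study. That would have force if the SAP were silent, but the table itself labels these deaths as on-study before censoring them.

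A reader might also infer three stronger claims. The documents do not support them.

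- *That the SAP makes salvage treatment erase a documented progression.* The rows come in pairs, no therapy against therapy before the event, and the progression event rows use the first PD date. No row censors progression followed by therapy. This is a drafting gap, not a stated rule.
- *That censoring a progression first seen after new therapy breaches the protocol.* Section 9 and the Appendix E footnote give that censoring support. The definitions rely on Appendix E, so the point is unreconciled rather than plainly wrong.
- *That the two-assessment requirement, with visits 3 months apart off treatment, pushes relapsing patients into censoring.* Section 9 sets no minimum interval between the assessments, and the SAP takes progression as the investigator reports it. Nothing sends an unconfirmed progression to a censoring row.

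**Conclusion.** The point holds in two parts. First, the SAP table contradicts Protocol 10.4.2 and SAP 1.2 by censoring on-study deaths that follow subsequent therapy. This is a conflict of text and needs no assumption. Second, the table has no row for documented progression followed by therapy, which leaves the coding of a common path open.

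The upward bias is conditional. It requires that subsequent therapy be started because disease is returning, and the documents do not say why or how often it is started. The shift from 50% to about 53% or 57% rests on an assumed PFS rate, an assumed 10% or 20% of events censored, and a constant hazard. It illustrates the possible effect and does not forecast it. The effect falls on the 2-year and median PFS estimates only. The matter is worth correcting before analysis because the correction is small.

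**What to change.** Revise the PFS table in SAP section 5/6 as follows.

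1. Count death without prior progression as an event at the date of death, whether or not subsequent therapy was given.
2. Reword the condition in the event rows to no subsequent therapy before the event, so that progression followed by therapy is an event at the first progression date, whether the patient later dies or not.
3. State how a progression first seen after new therapy is handled, and reconcile the row with section 9 and the Appendix E footnote. If it does not count as progression, a later on-study death is still an event at the date of death.
4. Define on study and subsequent therapy, since both now decide outcomes and neither is defined.
5. Report the present new-therapy censoring as a labelled sensitivity analysis.

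The cost is SAP wording and one extra Kaplan-Meier run. Death dates are already needed for OS, and Protocol 7.4 and Appendix D already schedule response and survival follow-up. Appendix D has no line of its own for subsequent therapy, so the source of its start date should be confirmed; concomitant medication review continues in follow-up before progression. The PFS estimate may come out less favourable.
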